Cover page

Study Title: Evaluation of the Feasibility of a Mobile Phone-Based Intervention (Zalo Application) on Depression, Anxiety, and Stress Among Caregivers of Patients with Dementia

NCT: 04958707

Date of version: April 21, 2023

Evaluation of the Feasibility of a Mobile Phone-Based Intervention (Zalo Application) on Depression, Anxiety, and Stress Among Caregivers of Patients with Dementia.

1- Objectives

The study aims to:

- Identify the information and skills that caregivers of dementia patients need to develop intervention content.
- Assess the feasibility of the intervention and the feasibility of conducting a randomized controlled trial of a mobile phone-based intervention for dementia caregivers, including recruitment rates, retention rates, completion of outcome measures, and acceptance of the intervention.

2- Literature Review

The total number of dementia cases is projected to reach 82 million by 2030 and 152 million by 2050 (1). The prevalence of dementia among older adults is estimated to be 5-8% (1). In Vietnam, community-based studies in the northern and southern regions indicate a dementia prevalence of 4.8-5%, while a study in Hue found a rate of 9.4% in 2014 (2,3). Most dementia patients live at home and are cared for by family members (4). As the number of dementia patients increases, the demand for caregivers rises. However, most caregivers lack adequate knowledge and support to fulfill their role. Dementia caregiving imposes significant psychological burdens, such as depression, anxiety, and stress, alongside physical and economic burdens. Studies indicate that caregivers of dementia patients experience significantly higher stress levels than caregivers of non-dementia patients and exhibit higher rates of depression and physical health problems. (5-7). Meta-analysis findings suggest that the prevalence of depression and anxiety among caregivers is 34% and 44%, respectively. These factors negatively impact caregivers' well-being, leading to poor quality of care and potential neglect of patients. Therefore, interventions targeting caregivers of dementia patients are essential to reducing psychological burdens and improving the quality of life for both caregivers and patients (8-11).

Information technology is considered a promising solution that can provide caregivers with benefits such as disease information, communication platforms, forums, and social support. Mobile phones are widely used in Vietnam. Research by Tremont has shown that using mobile phones reduces psychological burdens such as depression, anxiety, and stress among dementia caregivers while improving their ability to cope with patients' behavioral disorders. Other studies have demonstrated that video-based interventions providing exercise information and daily activity support reduce caregiver depression and anxiety while increasing caregiver satisfaction (12-16).

3- Inclusion and Exclusion Criteria

Inclusion Criteria:

Aged ≥ 18 years, the primary caregiver of a dementia patient for at least the past 6 months, and will continue caregiving for the next 6 months of intervention; Dementia patients are diagnosed according to DSM-5 criteria and are community-dwelling.

Able to read and understand Vietnamese and willing to participate in the study;

Owns a smartphone with the Zalo app installed or is willing to install Zalo (short training on using Zalo will be provided).

Exclusion Criteria: Caregivers with severe chronic illnesses preventing them from fulfilling study requirements, such as metastatic cancer, vision or hearing impairments, or cognitive impairment (Mini-Cog score <4).

Consent Procedures:

Eligible caregivers will be informed about the study. If interested, they will be provided with written consent forms.

A screening log will document non-eligible participants or those who decline participation.

4) Study Outcomes

Primary outcomes include recruitment rates, retention rates, completion of outcome measures, and acceptance of the intervention.

5) Study Phases and Methodology

Phase 1: In-depth interviews with 20 caregivers at the Geriatrics Department of Gia Dinh People's Hospital. Interviews will be audio-recorded, transcribed in Vietnamese, and analyzed thematically using NVivo software.

Phase 2: A parallel-group randomized controlled trial (RCT) with 60 participants randomly assigned to the intervention group or control group (1:1 ratio). Outcome measures will be assessed at baseline, immediately post-intervention, and three months post-intervention.

Randomization: Participants will be assigned using block randomization (block size = 4) by an independent statistician. Outcome assessors will be blinded.

Intervention Group: Participants will be added to a Zalo group managed by a researcher. Weekly, the researcher will post a topic determined from Phase 1 findings. Caregivers will be encouraged to discuss and share experiences.

Control Group: Participants will be directed to the Alzheimer's Association website for reliable information.

Psychological Distress Monitoring: Stress levels will be assessed biweekly using a stress thermometer. If a participant scores >4, they will be asked if they wish to continue.

6) Data and/or Sample Management and Security

Data Analysis

Phase 1: We will use Nvivo version 12 to manage data and code interview transcripts in Vietnamese. We will conduct content analysis, including data coding and category development.

The analysis will begin by identifying emerging concepts during the open coding process. The principal investigator will complete the coding with collaboration from two other researchers. The researchers will independently check and code the data, then discuss and refine it until consensus is reached. Final categories will be constructed, and all data will be reviewed and sorted into relevant categories. The data will be analyzed by the Vietnamese research team and later reviewed by two experienced qualitative researchers (one bilingual in Vietnamese and English) in Australia to establish higher-level categories and finalize the analysis. The most common issues caregivers need information and support for will be identified to develop interventions in Phase 2.

Phase 2: We will use Stata version 14 (StataCorp, College Station, TX, USA) for data analysis. Continuous variables will be presented as mean and standard deviation if normally distributed or as median and interquartile range if non-normally distributed. The recruitment rate, retention rate, and completion rate of outcome measures will be presented as percentages.

Data will be collected by trained researchers from the research team. Researchers involved in data analysis will have access to the data.

The information collected from this study will be kept confidential. All personally identifiable information of participants will be replaced with numerical codes. The de-identified study data will not be shared or provided to anyone except the study sponsor and the data safety monitoring committee. The data will be stored in a locked cabinet at the Department of Geriatrics - University of Medicine and Pharmacy, Ho Chi Minh City. Raw data will be collected using data collection forms and stored in a locked cabinet until analysis. Afterward, baseline and follow-up data will be entered into a secure, password-protected database by the research team.

7) Data and/or Sample storage

The data will not be stored for future use.

8) Data Monitoring Regulations to Ensure Participant Safety

Definition of Adverse Events, Severity, and Relevance

Adverse events are defined as any medical or health-related incident that is undesirable or harmful to the participant, occurring temporarily in connection with their participation in the study, regardless of whether it is considered related to the study participation.

Serious adverse events include any adverse event leading to death, life-threatening conditions, requiring or prolonging hospitalization, causing disability or significant long-term impairment, or any other condition that researchers consider to represent a significant risk.

Severity classification of adverse events:

Mild: Symptoms that do not require medical treatment or evaluation; transient signs and symptoms that do not affect normal activities.

Moderate: Events causing minor inconvenience or concern to participants and may interfere with daily activities but typically improve with simple treatment; moderate adverse events may cause some functional impairment.

Severe: Events that disrupt participants' normal daily activities, often requiring medical treatment and leading to functional incapacity.

Likelihood of adverse events:

Unexpected: The nature or severity of the event does not align with known information about the studied condition or intervention in the protocol, consent form, product documentation, or investigator materials.

Expected: The event is considered related to the intervention or the studied issue.

Relevance of adverse events to study participation:

Definitely related: The adverse event is linked to the research procedure—occurs in a reasonable sequence after the intervention, follows a known or expected reaction pattern, improves when the intervention is discontinued, and reoccurs with re-exposure. This adverse event cannot be reasonably explained by any other clinical characteristics of the participant.

Possibly related: The adverse event occurs in a reasonable time sequence following the intervention and follows a known or expected reaction pattern, but it may also be caused by other factors.

Unrelated: The adverse event is not related to the intervention—another cause is identified, and/or the timing of the event does not clinically align with the intervention, and/or the causal relationship is biologically implausible.

Reporting of Adverse Events

The method for reporting adverse and serious adverse events includes:

No serious adverse events are expected based on the nature of the intervention (i.e., behavioral, minimal risk), and no adverse events have been reported in caregiver intervention literature in Vietnam.

All serious adverse events (SAEs) and unexpected events (i.e., not previously reported for this intervention) will be reported to the IRB, NIA PO, and Safety Officer (SO) within 48 hours of becoming aware of the event. Additionally, all cases of death (expected or unexpected) will be reported within 24 hours to the IRB, NIA PO, and Safety Officer. A summary of all other SAEs will be reported to the NIA Program Officer and Safety Officer quarterly, unless otherwise required by the SO.

A standard form, either in paper or electronic format, will be used to document and record all reports of adverse and serious adverse events following the study protocol (from the start of the intervention to the completion of study participation).

Adverse events will be reported according to UC Davis IRB policies. They will also be reported to the NIA Program Officer and Safety Officer during regular meetings (at least semi-annually) and in annual progress reports.

9) Withdrawal from the Study

Participants may withdraw from the study at any time if they choose. We will ask them for their reason for withdrawing, should they wish to share, but no further data will be collected from them.

10) Risks to Participants

Potential risks to participants (caregivers of dementia patients) include psychological stress related to completing questionnaires and/or the intervention, as well as loss of confidentiality.

11) Potential Benefits to Participants

Potential benefits to participants include reduced psychological stress, decreased caregiver burden, improved knowledge, increased confidence in their abilities, and enhanced understanding of dementia.

12) Community Participation in the Study

This study involves hospital participation. The participants are caregivers of dementia patients treated at the Department of Geriatrics – Nhan dan Gia Dinh Hospital.

13) Sharing Results with Participants

The knowledge gained from this study will not be shared with participants before being widely disseminated to the public.

14) Ethics in Research

The study has been approved by the Ethics Committee - University of Medicine and Pharmacy, Ho Chi Minh City and is pending approval from NIA. The study will commence after receiving approval from NIA.

15) Measures to Protect Participants' Privacy

Participants will interact with one or two researchers from our study team. If they do not wish to post questions in the group chat, they may send private messages to the researcher.

To ensure participant comfort, we will explain the risks and benefits of the study. In Phase 1, participants will be interviewed by a trained researcher who will be empathetic and create a supportive environment during in-depth interviews.

In Phase 2, before intervention content is posted in the group chat, we will ask participants about their availability.

Within the research team, three researchers involved in in-depth interviews and data analysis will be allowed access to participant information. Any other team members wishing to access participant information must obtain approval from the principal investigator.

16) Compensation for Study-Related Injuries

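### Should the caregiving criterion run to the last assessment, three months after the intervention, rather than to the end of the intervention?

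*Combined protocol and SAP*

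**What the plan says.** Section 3 (Inclusion and Exclusion Criteria) looks both ways in time. The participant must have been "the primary caregiver of a dementia patient for at least the past 6 months", and must be someone who "will continue caregiving for the next 6 months of intervention". The second phrase is the only place where the documents give a length for the intervention.

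Section 5 (Study Phases and Methodology), Phase 2, has "60 participants randomly assigned to the intervention group or control group (1:1 ratio") and sets the schedule: "Outcome measures will be assessed at baseline, immediately post-intervention, and three months post-intervention". The description of the intervention arm gives a frequency but no total duration: "Weekly, the researcher will post a topic determined from Phase 1 findings".

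Section 4 (Study Outcomes) lists what the trial is to measure: "Primary outcomes include recruitment rates, retention rates, completion of outcome measures, and acceptance of the intervention". The Phase 2 analysis text in Section 6 reports the recruitment, retention and completion rates as percentages and describes no between-arm test.

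Section 9 (Withdrawal from the Study) covers departure by choice only: "Participants may withdraw from the study at any time if they choose". It says nothing about a participant whose caregiving has ended, and no section records caregiving status after entry.

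**The concern.** Set side by side, the criterion and the schedule seem to have different end points. The forward-looking criterion stops when the intervention stops, and the last assessment comes three months later. A caregiver who already knows that the patient will move into residential care, or pass to another relative, at month 7 meets the criterion and still has a visit due at month 9.

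Two things could be at stake. First, retention and completion of outcome measures are primary outcomes. Loss because the caring role ended points to a different design response from loss because the intervention was unwelcome. Second, distress scores at the last visit could mix current and former caregivers, with nothing in the data to tell them apart.

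There is also a question about the wording. If 6 months was meant to span the whole study, with 3 months of intervention and 3 of follow-up, the criterion misstates the intervention length.

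**Working it through.** **Inputs.** The forward caregiving period is 6 months (Section 3). The last assessment is 3 months after the intervention ends, and the Phase 2 sample is 60 (both Section 5). The documents give no total follow-up time, rate of caregiving ending, expected attrition or retention target, so there is no figure of the plan's own to reproduce.

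**Timeline.** Let D be the intervention length in months. The last assessment falls at D + 3. The months beyond the criterion are max(0, D + 3 − 6), and their share of follow-up is that number divided by D + 3.

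| D | Last assessment (month) | Months beyond criterion | Share |
|---|---|---|---|
| 3 | 6 | 0 | 0% |
| 4 | 7 | 1 | 14.3% |
| 5 | 8 | 2 | 25.0% |
| 6 (literal text) | 9 | 3 | 33.3% |

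The literal reading gives the 3 uncovered months. A 3 + 3 reading gives none, but no section supports it.

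**How many people.** Assume a constant monthly rate h of caregiving ending. These rates are assumptions and do not come from the documents. The proportion stopping in any 3-month window is 1 − (1 − h)³. Applied to all 60, this gives:

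- h = 1%: 1 − 0.99³ = 2.97%, or 1.8 people
- h = 2%: 1 − 0.98³ = 5.88%, or 3.5 people
- h = 3%: 1 − 0.97³ = 8.73%, or 5.2 people

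That count is too high, because some will already have stopped by month 6. The proportion stopping in months 0 to 6 is 1 − (1 − h)⁶, and the number stopping in months 6 to 9 is 60 × (1 − h)⁶ × [1 − (1 − h)³]:

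| h per month | Stop in months 0–6 | Stop in months 6–9 |
|---|---|---|
| 1% | 5.9% (3.5 of 60) | 1.7 of 60 |
| 2% | 11.4% (6.9 of 60) | 3.1 of 60 |
| 3% | 16.7% (10.0 of 60) | 4.4 of 60 |

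**What a longer criterion could remove.** An entry criterion records an expectation and can exclude only endings foreseen at entry. If f is the foreseeable share, a 9-month criterion removes f × 1.7 to f × 4.4 people, with f unknown and between 0 and 1. Unforeseen endings, such as the patient's death, happen under either wording. At every assumed rate, about twice as many people stop before month 6 as between months 6 and 9, and a longer criterion does nothing about unforeseen endings in either period.

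**Do the passages conflict?** One limits who may enter, by the role expected while the intervention runs. The other says when people are measured. Neither says that only current caregivers are to be measured, so both can hold at once.

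**The case for a change.** The best case for a change is that the sponsor itself made continued caregiving a condition of entry and then left the final assessment outside it. Retention and completion are primary outcomes. Section 9 asks for a reason for withdrawal only if the participant wishes to give one, so the plan cannot reliably separate loss caused by the end of the role from loss caused by the intervention. Former caregivers who stay in the study would not be identified at all. On the 3 + 3 reading, the only statement of intervention length is wrong. A caregiving-status item at each visit would cost almost nothing.

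Part of this stands. Section 5 should state the intervention length, and a status item with a breakdown by continuing caregiving would help in describing the last visit. These add detail and do not repair a fault.

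The rest does not stand. No section treats the end of caregiving as loss, so a former caregiver who attends the visit counts as retained and the retention percentage is correct as it is. Section 4 does not tie retention or completion to the last visit alone. Distress scores are not primary outcomes, and endings unrelated to allocation would be expected in both randomised arms. The number affected cannot be compared with the attrition the trial expects, because the documents give no such figure.

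Lengthening the criterion also has a price. It narrows the eligible pool when recruitment is a primary outcome, and it screens out attrition that a feasibility trial is meant to reveal.

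**Conclusion.** No change to the plan follows. On the literal text, the last assessment falls at month 9 and the caregiving expectation ends at month 6, leaving 3 of 9 months uncovered. This is a tenable choice and not a contradiction, and the planned percentages remain sound. Whether to extend the criterion to month 9 is a trade-off between a more uniform group at the last visit and a pool and attrition rate closer to practice. For a feasibility trial of 60, keeping the shorter criterion is reasonable.

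The size rests on two assumptions: that the intervention lasts 6 months, which is inferred from a phrase in the eligibility criterion, and that caregiving ends at a constant 1% to 3% per month. On those, about 2 to 4 of 60 would stop between months 6 and 9, and a longer criterion would prevent only the foreseeable part, which the documents do not allow anyone to estimate. If the intervention lasts 3 months, the gap is zero. The missing statement of intervention length in Section 5 is a detail that the study team can supply, and recording caregiving status at each assessment is a sensible option.

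### The stress prompt does not say what a caregiver would be continuing, and the only exit described ends all data collection, so someone who wants to leave only the Zalo group may also be lost to follow-up

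*Combined protocol and SAP*

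**What the plan says.** Section 5, Psychological Distress Monitoring, has participants rate their stress biweekly on a stress thermometer. The action on a high score is: "If a participant scores >4, they will be asked if they wish to continue". The text does not name what is being continued, say what follows a refusal, or limit the check to one arm.

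Section 9 allows withdrawal from the study at any time. The team asks for a reason, "should they wish to share, but no further data will be collected from them". No other way of stopping is set out in the visible text; the consent pages are not available.

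Section 4 states: "Primary outcomes include recruitment rates, retention rates, completion of outcome measures, and acceptance of the intervention". On timing, Section 5 states: "Outcome measures will be assessed at baseline, immediately post-intervention, and three months post-intervention". The Phase 2 analysis in Section 6 says: "The recruitment rate, retention rate, and completion rate of outcome measures will be presented as percentages".

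Three other places bear on how the prompt should be read:

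- Section 1 has a double aim: "Assess the feasibility of the intervention and the feasibility of conducting a randomized controlled trial".
- Section 10 lists among the risks "psychological stress related to completing questionnaires and/or the intervention".
- Of the control group, Section 5 says: "Participants will be directed to the Alzheimer's Association website for reliable information".

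**The concern.** Asking a distressed caregiver whether to go on is a sound welfare check and should stay. The difficulty is that one yes/no question covers two different decisions. A caregiver may find the group a burden and still be willing to complete two follow-up assessments, or the reverse. Section 10 recognises both sources of stress, and a single answer cannot show which one the caregiver wants to be rid of.

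Staff must do something with each refusal, and the only written procedure ends data collection. If they follow it, the trial loses assessments that the caregiver might have given willingly, and loses them among caregivers selected for high stress. It also blurs the double aim in Section 1. Leaving the group but attending assessments is evidence against the intervention's feasibility and in favour of the feasibility of running an RCT. Handled as full withdrawal, it counts against both. The team planning the later trial would then see lower retention and completion than the procedure needed to produce.

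**Working it through.** The plan gives no retention target, expected dropout, rate of scores above 4 or sample size derivation, so there is no stated figure to reproduce. The check is a reading of the text followed by simple proportions.

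**Reading**

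1. The prompt is addressed to any participant. Controls are only pointed to a website and have no group to leave. A question put to both arms is therefore most naturally about continuing in the study.
2. The only described exit from the study is Section 9, and it ends data collection.
3. Steps 1 and 2 together mean that a refusal forfeits the remaining outcome assessments. This is an inference; no sentence says it.
4. The prompt recurs. If biweekly means every two weeks, and monitoring lasts for the 6 months of intervention mentioned in the inclusion criteria (about 26 weeks), there are about 26/2 = 13 checks per caregiver. Both conditions are assumptions, because the monitoring period is not stated.

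**Cost of one exit**

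Inputs from Section 5: 60 participants, 1:1 allocation, block size 4, and two follow-up assessments.

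- Blocks: 60/4 = 15 complete blocks of 2:2, so 30 per arm.
- Planned follow-up assessments: 60 × 2 = 120 overall, 30 × 2 = 60 per arm.
- Retention: 1/60 = 1.7 points overall, 1/30 = 3.3 points in the arm.
- Completion, exit before the post-intervention visit (both follow-ups lost): 2/120 = 1.7 points overall, 2/60 = 3.3 points in the arm.
- Completion, exit after that visit, if monitoring runs on that long (one lost): 1/120 = 0.8 points overall, 1/60 = 1.7 points in the arm.

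**Scale illustration, not an estimate**

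Assume 3 unrelated losses in each arm, and k intervention-arm caregivers who want to stop only the Zalo group, do so before the post-intervention visit and would still attend assessments.

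| k | Arm retention if still followed | Arm retention if withdrawn (Wilson 95% CI) | Overall retention if withdrawn | Follow-up assessments lost |
|---|---|---|---|---|
| 0 | 27/30 = 90.0% | 27/30 = 90.0% (74.4 to 96.5) | 54/60 = 90.0% | 0 |
| 1 | 27/30 = 90.0% | 26/30 = 86.7% (70.3 to 94.7) | 53/60 = 88.3% | 2 |
| 3 | 27/30 = 90.0% | 24/30 = 80.0% (62.7 to 90.5) | 51/60 = 85.0% | 6 |
| 5 | 27/30 = 90.0% | 22/30 = 73.3% (55.6 to 85.8) | 49/60 = 81.7% | 10 |

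At k = 3 the handling rule alone moves arm retention by 3/30 = 10 points and overall retention by 3/60 = 5 points, and loses 6/120 = 5% of follow-up assessments.

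**The case against.** The strongest reply is that the harm is inferred. Nothing links a refusal at the prompt to Section 9, and the consent form, where staged options might appear, cannot be seen. Section 16 (Compensation for Study-Related Injuries) speaks of study-related stress in the intervention group; if the checks were meant for that arm alone, the question could be about the Zalo group only. The causality definition in Section 8 refers to an event improving once the intervention is stopped, which presupposes that stopping can be observed. These points stand, and they are why the conclusion is conditional. None of them supplies a procedure for staff who receive a refusal.

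A second reply is that caregivers can already step back informally. Discussion in the group is only encouraged, and Section 15 (Measures to Protect Participants' Privacy) allows private messages instead. That reduces the number affected, but a caregiver who is asked directly and declines is no longer stepping back informally.

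A reader might also infer that exits following the prompt would be merged beyond recovery with other losses. The documents do not support that. Section 9 asks for a reason, though giving one is voluntary, and the biweekly scores would show whether an exit followed a high score. Acceptance is already a separate primary outcome, so rejection of the group has a place to be reported. Nor does silence on percentages by arm show that the arms will be pooled; that is ordinary missing detail and not part of this point. What those records cannot recover is the assessments never taken.

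Finally, 1/60 and 1/30 are the cost of any dropout in a trial of this size. True. The avoidable part is limited to caregivers who score above 4, decline, want to stop only the group and would still be assessed. The documents give no rate for any of these steps.

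**Conclusion.** The point holds as a conditional one and is worth acting on. What the caregiver is asked to continue is undefined, and the only written exit ends data collection. On the natural reading, the most stressed caregivers are repeatedly offered a way out that takes their remaining assessments with it. Each avoidable exit costs 1.7 points of overall retention or 3.3 points in its arm, and up to two follow-up assessments. The total cannot be stated.

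This rests on two assumptions: that a refusal is handled under Section 9, and that some caregivers who decline would still agree to be assessed.

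Three stronger conclusions are not supported: that the plan declares a refusal to be a withdrawal, that retention will be distorted by a known amount, or that the welfare check itself is at fault. Exits after the prompt remain a genuine feasibility result. The planned Phase 2 analysis is descriptive, so no hypothesis test or power claim is affected; the loss is of follow-up data and of clarity about what was rejected.

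**What to change.** Keep the question after a score above 4, but put it as two separate choices in Section 5: whether to stop the Zalo group (or the control activity), and whether to stop the outcome assessments. In Section 9, apply the end of data collection only to those who decline further assessment, and keep full withdrawal open at any time. If the consent form already offers staged options, state the same options in Sections 5 and 9.

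Count a caregiver who leaves the group but attends assessments as retained, and report the stop under acceptance of the intervention. Use the reason that Section 9 already requests, together with the biweekly scores, to identify exits that followed a prompt, and keep counting them as a feasibility result.

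The cost is a wording amendment to the protocol, consent form and ethics submission. Section 14 says ethics committee approval has been given and that the study will start only after NIA approval, so on the document's own account the change could be filed before enrolment. The downside is slightly more optional contact with distressed caregivers, which they can refuse.
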